**28. Critical major bleeding at 28 days**

- At 28 days, a binary indicator of any major bleed (fatal or in critical area or organ) or death.

**29. Categorization of the primary endpoint - organ support free days**

- Three-level outcome: No organ support without death, some organ support without death, death

**30. Four-level organ support**

- Four-level outcome: No organ support without death, some organ support without invasive mechanical ventilation and without death, some invasive mechanical ventilation without death, death

**31. Categorization of the endpoint–invasive mechanical ventilatory support free days**

- Three-level outcome: No invasive mechanical ventilatory support without death, some invasive mechanical ventilatory support without death, death
- HFNO is not counted as ventilatory support

**32. Major Thrombotic or Bleeding Composite Event by Day 28**

- At 28 days, a binary indicator of
  - Death or
  - Major thrombotic event or
  - Critical major bleed (fatal, ICH, Bleeding in critical area or organ)

**33. Composite Thrombotic or Bleeding Event by Day 28**

- At 28 days, a binary indicator of
  - Death or
  - Any thrombotic event (major thrombotic event or DVT) or
  - Major ISTH bleed

**34. EQ-5D**

- At 90 days, continuous measure of function

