## 7. Endpoints

The following endpoints will be analyzed, displayed graphically, and summarized with descriptive statistics.

1. **Organ Support-Free Days (OSFDs)**
  - This is the primary endpoint for the study, and is a composite ordinal endpoint reflecting the number of days alive and off organ support, with in-hospital mortality from any cause as the worst possible outcome. Organ support considered is cardiovascular (vasopressor/inotrope support) and respiratory support (high flow nasal cannula, invasive or non-invasive ventilation, or ECMO).

In-hospital death is considered a -1 and may occur after study day 21 as long as it occurs during the index hospitalization through day 90.

- Detailed definitions for OSFDs are specified in the study data dictionary.
- Missing values for organ support-free days will be treated as “missing and will not be included in the analyses”. We will conduct a sensitivity analysis on the primary endpoint treating missing values using the “last known status carried forward” approach.

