## 5. **Vasopressor/inotrope-free days to day 28**

- An ordinal outcome of the number of days alive and free of vasopressor/inotropes. This is the exact calculation of OSFD, with vasopressor/inotropes as the only organ support category. In-hospital death is considered a 0 (consistent with ACTIV-4A protocol 1.0).
- All platforms compute vasopressor-free days based on integer days on which vasopressors/inotropes were not received at any time
- Vasopressor/inotrope-free days will be computed based on the duration of time from the initiation of vasopressors/inotropes to the final cessation of vasopressors/inotropes during the 28-day period; intervening days on which patients are not on vasopressors/inotropes will be ignored

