**35. Symptoms**

- Binary indicator of any of the following symptoms: fatigue, cough, dyspnea, and chest pain.
- Repeat analysis for each individually
- At 90 days
- Among those that did not have the symptom prior to COVID-19 illness based on the appropriate eCRF

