### [12.8. Exploratory Analyses](#)

Exploratory analyses after unblinding will not be considered inferential and no p-values will be presented. Any post-hoc exploratory analyses will use the following methods:

1. Ordinal endpoints will be compared using a cumulative proportional odds model with summaries of the OR, 95% confidence intervals, and Wilcoxon tests for robustness against a lack of proportional odds.
2. Time-to-Event analyses will utilize a Cox proportional hazards model, summarizing the hazard ratios and 95% confidence intervals.
3. Continuous endpoints will compare means with 95% confidence intervals based on two-sample t-test procedures.
4. Dichotomous proportions will be compared using logistic regression summarizing the OR and 95% confidence intervals. Differences between proportions will be summarized using observed differences and normal approximations for the 95% credible intervals.

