#### [12.9. Handling of missing data](#)

For the primary endpoint of OSFDs missing primary outcomes will be ignored. A sensitivity analysis is conducted where last status carried forward is used for imputation. Patients with missing age, date of randomization, sex or treatment assignment will be ignored. For additional endpoints those patients missing the endpoint will be ignored (for time to event analyses censoring will be used and aren't considered missing). For the subgroup analyses patients with missing subgroup variables will be lumped into a single group of "missing" in addition to the subgroup classifications.

For time-to-event analyses patients that have a competing event that dictates they cannot achieve a positive outcome (like death for time to hospital discharge), the patient will be assigned a no positive event outcome at the maximum time for the analysis. Patients not achieving an absorbing event that become lost-to-follow up will be censored at the last known time (unless otherwise specified for the analysis).

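### The SAP has no rule for death before day 90 in the EQ-5D and symptom endpoints, and its missing-data default would in effect limit both to survivors

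*SAP*

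**What the plan says.** Endpoint 34 in SAP section 7 has a one-line definition: "At 90 days, continuous measure of function". Endpoint 35 is a "Binary indicator of any of the following symptoms: fatigue, cough, dyspnea, and chest pain", also at 90 days and then repeated for each symptom. Its only restriction is "Among those that did not have the symptom prior to COVID-19 illness based on the appropriate eCRF". Neither definition mentions death.

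Two rules in SAP 12.9 might apply. The general one is "For additional endpoints those patients missing the endpoint will be ignored". The one that deals with death as a competing event begins "For time-to-event analyses patients that have a competing event that dictates they cannot achieve a positive outcome", so it does not reach a continuous score or a binary indicator.

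The only method given for continuous endpoints is in SAP 12.8: "Continuous endpoints will compare means with 95% confidence intervals based on two-sample t-test procedures". That section covers post-hoc exploratory work and is silent on death. The marginal structural models in SAP 12.11 address departures from assigned treatment, not death.

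Other endpoints do count death. For organ support-free days, "In-hospital death is considered a -1 and may occur after study day 21". Vasopressor-, ventilator- and renal replacement-free days score it 0. Deaths are carried to 90 days without the good outcome in ICU liberation and hospital stay. Death is also a component or a level of the composite and ordinal endpoints.

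**The concern.** A patient who dies before day 90 has no EQ-5D score and no symptom report. With no rule for death, the natural application of 12.9 is to drop that patient along with someone who did not answer the telephone. The two cases differ. Non-response hides a value that exists, whereas death is itself a result of the kind the trial aims to reduce.

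If the P2Y12 inhibitor changes mortality, the survivors in the two arms are differently selected groups. Suppose treatment saves some patients who are left frailer than average. The primary endpoint counts each of them as a gain, while the survivor-only EQ-5D lets the same patients lower the treated mean. If treatment raised mortality among frail patients, the distortion would run the other way and flatter the drug.

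**Working it through.** The documents give no mortality, EQ-5D or symptom assumption for these endpoints and no sample size for the P2Y12 comparison. There is therefore no planned figure to reproduce, and **every input below is an assumption**.

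**Set-up.** S_c and S_t are the proportions alive at day 90 under control and treatment. Treatment saves some patients and causes no deaths. It does not change function in patients who would survive in either arm (mean m). Saved patients have mean u.

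- Control survivor mean = m
- Treated survivor mean = [S_c·m + (S_t − S_c)·u] / S_t
- Survivor-only difference = treated survivor mean − m
- Difference with death scored 0 = S_t × treated survivor mean − S_c·m = (S_t − S_c)·u

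**One case in full.** Mortality 25% vs 20%, m = 0.75, u = 0.40:

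- Treated survivor mean = (0.75 × 0.75 + 0.05 × 0.40)/0.80 = 0.5825/0.80 = 0.728
- Survivor-only difference = 0.728 − 0.750 = −0.022
- Death scored 0: 0.5825 − 0.5625 = +0.020

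**Range for EQ-5D** (m = 0.75, u from 0.20 to 0.60):

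| Mortality, control vs treated | Survivor-only difference | Death scored 0 |
|---|---|---|
| 10% vs 7% | −0.018 to −0.005 | +0.006 to +0.018 |
| 25% vs 20% | −0.034 to −0.009 | +0.010 to +0.030 |
| 35% vs 28% | −0.054 to −0.015 | +0.014 to +0.042 |

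With u = 0.75, so that saved patients match other survivors, the survivor-only difference is 0.000 in every row.

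**Symptoms.** Assume a 40% symptom rate in patients who survive in either arm, 60% to 95% in saved patients, and mortality 25% vs 20%. An odds ratio above 1 means benefit, as in the SAP.

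- At 60%, the treated survivor rate is (0.75 × 0.40 + 0.05 × 0.60)/0.80 = 0.4125. The survivor-only OR is (0.40/0.60)/(0.4125/0.5875) = 0.95.
- Symptom-or-death is 0.25 + 0.30 = 0.55 in control and 0.20 + 0.33 = 0.53 in treated. The OR is (0.55/0.45)/(0.53/0.47) = 1.08.
- At 95%, the two odds ratios are 0.87 and 1.01.

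**Does scoring death 0 solve it alone?** Not if living non-responders are still dropped. Take 25% vs 20% mortality, m = 0.75 and u = 0.55. The treated survivor mean is (0.5625 + 0.0275)/0.80 = 0.7375, and the full-data difference with death scored 0 is 0.5900 − 0.5625 = +0.0275. Now let half the survivors in each arm respond:

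- Control = (0.375 × 0.75)/(0.375 + 0.25) = 0.28125/0.625 = 0.450
- Treated = (0.400 × 0.7375)/(0.400 + 0.20) = 0.295/0.600 = 0.492
- Difference = +0.042

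Deaths are over-represented, and the apparent benefit is about half as large again as the true +0.0275.

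**The case against.** The strongest objection is that the survivor-only analysis is inferred. A reader might take the SAP to specify a survivors-only analysis, or to class a death as a missing value. It does neither. It omits a rule for death in two endpoints and has a default that, read literally, would drop these patients. The sponsor may intend something else. This limits how the point can be worded, but an unwritten intention would still need writing down.

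The stakes are also low, and this stands in full. Neither endpoint is in the protocol's lists in 4.2.2 and 4.2.3. Day-90 quality-of-life collection is optional (Protocol 7.1.3 and the schedule footnotes). No statistical trigger and no expedited report in SAP 3.1 uses either endpoint. Mortality through day 90 is reported separately, so an alert reader could explain a lower survivor mean.

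Finally, lower function among survivors can be a true description of the survivors. That is so, but it is then not the effect of randomized treatment, and the SAP does not label it as descriptive.

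**Conclusion.** The point holds as a gap in the SAP. Endpoints 34 and 35 have no rule for death, and the 12.9 default would in effect restrict both to survivors. With 25% versus 20% mortality and the other assumptions shown, EQ-5D moves from between +0.010 and +0.030 (death scored 0) to between −0.034 and −0.009 (survivors only). A reversal of sign is therefore possible. It needs both a mortality difference and saved patients who are frailer than other survivors, and the documents establish neither.

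A reader might infer that the day-90 results will contradict the primary result, or that the trial's conclusions are at risk. The documents do not support that: organ support-free days already rank in-hospital death worst, and the superiority and futility triggers use that endpoint only. This is a minor but inexpensive improvement.

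**What to change.** - **SAP 12.9:** state that, for endpoints 34 and 35, death before day 90 is an outcome and not a missing value. Keep three groups apart: known dead, alive without a response, and vital status unknown.
- **Endpoint 34:** name the EQ-5D score to be used. Report an analysis with death scored 0 if it is the index, or given the worst rank otherwise. Handle living non-responders by weighting or multiple imputation, not by dropping them. Show the survivor-only result and day-90 mortality by arm beside it.
- **Endpoint 35:** for the any-symptom indicator, compare alive and symptom-free with symptomatic or dead. This requires pre-COVID symptom status at enrollment for patients who later die. The documents do not say when that form is completed, so the sponsor should confirm it. If the status is not available, report the survivor-only result beside mortality and label it non-randomized.

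Day-90 vital status is already a scheduled item in Protocol 7.1.3, so the EQ-5D change needs no new visit. It does need more than wording, because the weighting or imputation model must be specified and run. The death-inclusive results will be partly driven by mortality, which is why the survivor-only figures stay alongside. The rule should be added before unblinding.

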**35. Symptoms**

- Binary indicator of any of the following symptoms: fatigue, cough, dyspnea, and chest pain.
- Repeat analysis for each individually
- At 90 days
- Among those that did not have the symptom prior to COVID-19 illness based on the appropriate eCRF

## 8. Graphical Data Summaries

1. All ordinal endpoints will be plotted using stacked cumulative bar plots and cumulative probability plots.
2. All time-to-event endpoints will be plotted using Kaplan-Meier or cumulative incidence plots. Positive clinical event outcomes will be plotted as the cumulative rate of event, and negative events will be plotted as the cumulative rate of event-free.

## 9. Descriptive Statistics

1. Ordinal endpoints will be summarized by the cumulative frequency of each outcome. The 5th, 25th, 50th, 75th, and 95th percentiles will be summarized.
2. Dichotomous endpoints will be summarized by the proportion in each category.
3. Time-to-event outcomes will be summarized by the 2.5th, 10th, 25th, 50th, 75th, 90th, and 97.5th percentiles from the Kaplan-Meier or cumulative incidence estimates, as available.

## 10. Baseline Characteristics and Co-interventions

The following demographics will be summarized across arms. More may be added as baseline summaries: Age, sex, BMI, race, ethnicity, illness severity at admission, pre-existing conditions, baseline use of oxygen (no, 2L or less, more than 2L but less than 20 L/min, high flow) non-invasive ventilation, invasive mechanical ventilation, ECMO, vasopressors/inotropes, renal replacement therapy, and miscellaneous physiological values and inflammatory biomarker laboratory values (see Appendix A). P2Y12 (specific agent used) by the first full day will be compared between groups. Additionally, exposure to relevant drugs (e.g., aspirin, steroids, immunomodulatory therapies, anticoagulation drug and dose) prior to hospitalization, at baseline, and during the treatment period will be compared between groups.

## 11. Adherence

Adherence will be assessed based on the proportion of patients receiving a P2Y12 agent consistent with their randomly assigned strategy by the end of the first full study day after randomization.

## 12. Analytic Approach

Each inferential analysis will be done using a Bayesian model. Some default frequentist methods are used for exploration and description. A summary of the analyses methods is provided below. Events that occur at low frequency will be reported descriptively and not modelled.

### 12.1. Primary Analysis of Primary Endpoint

The **primary analysis model** is a Bayesian cumulative logistic model for the ordinal primary endpoint. The model is described below.

The primary endpoint has 23 possible ordered outcome values. Let the outcome for a patient labeled as  $Y_i$ , with possible values,  $-1$  (death),  $0, 1, \dots, 21$ . A cumulative logistic model is specified. The model is structured so that an  $OR > 1$  implies clinical benefit. The model has factors for:

1. Each level of the ordinal endpoint
2. Each global site, nested within country
3. Age;  $\le 39, 40-49, 50-59, 60-69, 70-79, 80+$
4. Sex

5. Time: 2-week epoch bins of time working backwards from the last enrolled patient.
6. Hx cardiovascular disease, including HTN, and/or diabetes
7. Severe/Moderate cohort
8. For severe (type of organ support, invasive mechanical ventilation vs. not)
9. For moderate (the amount of O2 required, no O2, > 0 but <= 2, >2)
10. An effect for each intervention; the effects for P2Y12 are nested across cohorts
11. All sites within a country that have <5 patients randomized will be combined into a single site within that country.
12. For the primary outcome, if there is an outcome in the ordinal scale that did not occur in the data, then that outcome will be combined the next worse outcome. This is done for model stability. For example, if the outcome 11 never occurred, then a combined outcome of 10 & 11 will be modeled for the analysis.
13. If analyzing a single cohort that does not allow for the hierarchical structure in the model, the hierarchical structure of the treatment parameters will be replaced by a standard normal prior unless otherwise specified.

The primary analysis model will be referenced with certain model assumptions for sensitivity analyses. For example, the “time effects” in the model could be assumed to be 0.

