Pulmonary embolism will be confirmed by chest CT with PE protocol, pulmonary angiography or ventilation-perfusion scan. Events may also be defined without this imaging by the care team, as evidenced by, for example, "clot in transit" on echocardiogram. If PE is diagnosed and treated without imaging due to imaging availability concerns or risk of exposure to SARS CoV-2, this will be classified as probable PE. Later imaging is preferable in these cases when possible.

Stroke/ Peripheral Arterial Systemic Thromboembolism

Stroke or systemic embolism as diagnosed by imaging (i.e., head CT, lower extremity CT angiogram) or deemed "highly-likely" by the provider based on physical examination (i.e., acute hemiplegia thought to be due to stroke, acute distal lower extremity hypoperfusion). Systemic thromboembolism may involve the retinal artery, spinal cord or other vascular beds. Classification of ischemic vs. other etiologies is based on neuroimaging. Venous sinus thrombosis will be included in the category of vascular occlusion/ischemic stroke on the venous side. Primary CNS hemorrhage: intracerebral hemorrhage, subarachnoid hemorrhage, subdural hematoma, and rarely epidural hematoma or spinal hematoma. Secondary hemorrhagic stroke: blood associated with an ischemic infarct.

ICU Level of care disease state (severe illness)

Defined as receipt of cardiovascular or respiratory organ support as defined in the 21-day organ support free days. ICU level of care is defined as being on invasive or non-invasive mechanical ventilation, high flow nasal oxygen, or vasopressor therapy or ECMO support.

Myocardial infarction

Myocardial infarction is defined according to the universal definition of MI, which excludes myocardial injury e.g., isolated elevation of cardiac troponin. MI must include rise and fall of cardiac troponin above the 99th percentile with at least one of the following: symptoms of acute ischemia, ECG changes consistent with ischemia, new/presumed new wall-motion abnormalities or other imaging evidence of MI, abnormal coronary angiography (e.g. identification of a coronary thrombus).

Acute Kidney Injury

Acute kidney injury after enrollment is defined by KDIGO criteria for Acute Kidney Injury in the setting of not meeting these criteria upon enrollment:

Modified Stages:

- Stage 2: Serum Cr 2.0–2.9 times baseline
- Stage 3: Serum Cr \geq 3.0 times baseline, OR Increase in serum creatinine to \geq 4.0mg/dl, OR Initiation of renal replacement therapy

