## 12.12. Heterogeneity of treatment effect

The heterogeneity of the treatment effect will be evaluated in the following a priori defined subgroups:

- Age (< 50 years, 50-70 years, > 70 years)
- Sex
- Invasive mechanical ventilation at baseline for severe cohort
- For moderate (the amount of O2 required, no O2, > 0 but <= 2, >2)
- Heparin dosing during day 1. Categorized as therapeutic if defined as therapeutic at any time during day 0 or 1.

Additional exploratory subgroup analyses will include the following:

- Race/Ethnicity
- D-dimer levels
- Markers of inflammation (CRP, ferritin)
- Baseline troponin
- BMI
- Shock (use of vasopressors or inotropes at baseline)
- Baseline chronic kidney disease
- Steroid administration for COVID-19 at baseline
- IL-6 inhibitor administration for COVID-19 at baseline
- If additional treatments are determined through other research to be beneficial before unblinding subgroups will be defined by those treatments.
- Sites with at least 80% ticagrelor use as assigned P2Y12 inhibitor vs. sites with less than 80% ticagrelor use
- Geographic (Europe, US+Canada, Central and South America)

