### **Stopping Rules for Efficacy**

The trial has been designed to separately test the efficacy of P2Y12 with respect to OSFD within two patient cohorts: patients with moderate or severe illness.

The P2Y12 arm will be declared superior to the usual care arm within a specific cohort if the posterior probability of superiority within the cohort is greater than 0.99.

There are no efficacy stopping boundaries for a cohort based on the key secondary endpoint of major thrombotic events or death. The key secondary endpoint is addressed only when futility has been declared for the organ-support free-day endpoint.

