## 13. Models reporting outlines

### 13.1. Primary analysis of OSFDs

Population	
------------	--

Endpoint	
Model	
Factors	

The following posterior probabilities will be reported for each subtype being reported:

Quantity of Interest	Posterior Probability
P2Y12 is superior to control	
P2Y12 is futile	
P2Y12 is inferior	

The following will be reported:

Odds Ratio Parameter	Mean	SD	Median	95% Credible Interval
Age < 39				
Age 40, 49				
Age 50, 59				
Age 70-79				
Age 80+				
Female				
Time epoch 1				
...				
Time epoch k-1				
Hx cardiovascular disease/diabetes				
Invasive medical ventilation (severe only)				
Oxygen >0 but <=2 (moderate only)				
Oxygen > 2 (moderate only)				
Country				
P2Y12				

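### The severe-cohort primary model adjusts for baseline organ support only as invasive ventilation yes/no; adding baseline vasopressor/inotrope use, already collected, would be a cheap improvement with a small gain in power

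*SAP*

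**What the plan says.** SAP 12.1 lists the factors of the primary model: site within country, age, sex, two-week epoch, history of cardiovascular disease or diabetes, cohort, one severity marker per cohort, and the intervention. The severe-cohort marker is "For severe (type of organ support, invasive mechanical ventilation vs. not". The moderate-cohort marker has three oxygen levels. The reporting shell in SAP 13.1 matches: its only severe-specific covariate row is "Invasive medical ventilation (severe only".

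Vasopressors appear elsewhere in four roles:

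- **Endpoint.** SAP 7, item 1: "Organ support considered is cardiovascular (vasopressor/inotrope support) and respiratory support".
- **Definition of the severe state.** Protocol Appendix 2: "ICU level of care is defined as being on invasive or non-invasive mechanical ventilation, high flow nasal oxygen, or vasopressor therapy or ECMO support".
- **Baseline data.** SAP 10 includes them in the baseline summary: "invasive mechanical ventilation, ECMO, vasopressors/inotropes, renal replacement therapy".
- **Analysis.** SAP 12.12 has them only among the additional exploratory subgroups: "Shock (use of vasopressors or inotropes at baseline".

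The SAP gives no reason for leaving them out of the primary model.

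**The concern.** Under item 8, a ventilated patient in shock and a ventilated patient with stable circulation have the same covariate value. If the first has the worse outlook, the model leaves explainable variation in the outcome.

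The consequence in a proportional-odds model differs from that in a linear model. Omitting a prognostic covariate does not widen the standard error of the treatment effect. It shrinks the estimated log odds ratio toward 0. Superiority requires a "posterior probability of superiority within the cohort is greater than 0.99", so a shrunken effect reaches that threshold a little less often at a given sample size. What is at stake is a small amount of power in the severe cohort, obtainable from data already on the case report form.

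**Working it through.** **Is there a figure in the plan to reproduce?** No. Protocol 8.6 leaves sample size to the arm appendix, Appendix 7 (A7.10) refers to the SAP, and the SAP states no sample size or power. Nor do the documents give the prevalence of baseline vasopressor use or its prognostic strength. Every numerical input below other than the trigger thresholds and the 1:1 allocation is therefore an assumption.

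**Method.** Compute the expected maximum-likelihood fit and the information matrix of a proportional-odds model with treatment and ventilation, with and without a vasopressor term, under 1:1 allocation. Then

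gain in effective sample size = (b₁/SE₁)² ÷ (b₀/SE₀)² − 1,

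where b is the treatment log-OR, 1 is the model with the term and 0 the model without it.

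**Set A.** Assumed: 35% ventilated; vasopressors in 55% of these and 8% of the rest; OR 0.4 for ventilation (below 1 means fewer free days); treatment OR 1.3. Vasopressor users are then 0.35 × 0.55 + 0.65 × 0.08 = 24.5% of severe patients, of whom 0.65 × 0.08 = 5.2 percentage points are not ventilated.

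| Vasopressor OR, given ventilation | Gain | Per 1,000 severe patients (assumed N) |
|---|---|---|
| 1.0 | 0% | 0 |
| 0.6 | 1.2% | 12 |
| 0.5 | 2.3% | 23 |
| 0.4 | 3.9% | 39 |
| 0.3 | 6.6% | 66 |

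At OR 0.3 the treatment log-OR is 0.252 without the term and 0.262 = ln 1.3 with it. The coefficient alone would give (0.262/0.252)² = 1.081. The net ratio is 1.066, so the squared standard error rose by 1.081/1.066 = 1.014, and the standard error by about 0.7%. The gain is reduced attenuation, partly offset by a slightly larger standard error.

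**Set B.** Assumed: 23 levels; treatment OR 1.5; ventilation triples the odds of a worse outcome; 20% or 50% ventilated; vasopressors in 30-70% of ventilated and 3-5% of other patients. Power is at one-sided 0.01, as the analogue of the 0.99 rule, with N set to give 80% without the term.

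| Factor on odds of a worse outcome | Gain | Power with the term |
|---|---|---|
| 1.0 | 0% | 80.0% |
| 1.5 | 0.4-0.9% | 80.2-80.4% |
| 2.0 | 1.1-2.6% | 80.5-81.1% |
| 3.0 | 2.5-6.1% | 81.1-82.6% |

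For factors 1.5-3.0 the standard error rises by 0.02-0.7%, and a true OR of 1.50 is estimated as 1.478-1.499 when the term is omitted. At the top of the range, (ln 1.500/ln 1.478)² ÷ 1.0070² − 1 = (0.4055/0.3907)² ÷ 1.0140 − 1 = 6.2% from these rounded inputs, or 6.1% unrounded.

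**The two triggers** (normal approximation).

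- Superiority requires b/SE > 2.326. Omission lowers b proportionally more than it lowers SE, so a real effect crosses slightly less often. At a true OR of 1, b is centred on 0 in both models and the crossing probability is 0.01 in both.
- Futility requires b + 1.645 SE ≤ ln 1.2 = 0.182. Omission lowers both b and SE, so this is met slightly more often. With the Set A inputs, vasopressor OR 0.3, true OR 1.1 and N = 1,000, the probability is about 19-20% without the term and 18-19% with it.

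**The case against.** The case against has four parts.

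- **The plan already adjusts for a good deal.** Item 8 is a severity marker specific to the severe cohort, and the model also carries age, sex, site, epoch and cardiovascular or diabetic history. Neither calculation includes those terms, so the true gain could differ. This stands and is a reason for modest wording.
- **Being part of the endpoint does not make vasopressor use prognostic.** Protocol Appendix 2 counts free days only before the first and after the last use of any support. For a ventilated patient, vasopressors reduce the score mechanically only if they outlast ventilation. This stands. Added value given ventilation is plausible but not shown in the documents, and so the range starts at 0%.
- **The change is not free.** SAP 12.6 names sparse covariates as a source of sampler instability, and vasopressor use without ventilation is a small cell (5.2% in Set A). SAP 12.9 has no missing-data rule for baseline organ support. Both stand, but the cost is small: a yes/no term under an N(0,1) prior is well behaved beside nested site and epoch effects, and item 8 needs a missing-data rule anyway.
- **One model drives all adaptations, with roughly monthly analyses.** The covariate list should not change in response to accumating data. This governs when and by whom the change is made; it is not an argument against making it before unblinding.

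A reader might infer more than the documents support: that precision is being lost (the standard error is slightly smaller without the term), that both triggers become harder to reach (futility becomes easier), or that the randomized comparison is biased or the superiority trigger invalid (at no effect, neither changes).

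**Conclusion.** The point holds as a minor efficiency improvement. The factual part is clear from the SAP: one binary support factor for the severe cohort, and no vasopressor term in either the factor list or the results shell.

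The size is conditional. If vasopressor use roughly doubles the odds of a worse outcome given ventilation, adding it is worth about 1-3% of effective sample size, or 0.5-1.1 power points from 80%. Reaching 6-7% requires a conditional OR near 0.3. If it adds nothing beyond ventilation, the gain is nil. These figures rest on assumed prevalences, prognostic strengths and outcome distributions.

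The documents do not support calling the omission an error or a threat to validity. Nor do these calculations establish a need to separate non-invasive ventilation from high-flow oxygen; neither set includes that split.

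**What to change.** Before unblinding:

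1. Extend SAP 12.1 item 8 so that the severe cohort is adjusted for invasive ventilation (yes/no) and baseline vasopressor/inotrope use (yes/no). Give the new term the N(0,1) prior that Protocol 8.3 sets as the default for additional covariates. State the prior explicitly, because SAP 12.4 gives unspecified variables in the time-to-event models a standard deviation of 10.
2. Add the corresponding row to the SAP 13.1 table.
3. Carry the term into the secondary models that reuse the primary factors.
4. Add to SAP 12.9 how a missing baseline support value is handled, for example as its own category.
5. If interim analyses have already been run, have the change decided and dated by people without access to results by arm.

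If the sponsor prefers to keep item 8 as it stands, one sentence of justification would suffice. Splitting non-invasive ventilation from high-flow oxygen is optional.

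The cost is one or two more coefficients, a missing-data rule and a small cell of vasopressor use without ventilation, which the prior stabilises. No new data collection is needed.
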